4.1.2 Treatment Stage

The total duration of the Treatment Stage will be approximately 24 weeks.

In the part 1 of the study, on Day 1, subjects will be treated with any design of LYR-220 bilaterally. The LYR-220 insertion procedure will be assessed and optimized, if necessary, before the randomized part 2 phase. [Note: Subject enrollment in part 2 can begin after subjects in part 1 have undergone the LYR-220 insertion procedure; subjects in part 1 do not need to complete a certain amount of follow-up prior to part 2 commencing.] In the part 2 of the study, on Day 1, before any treatment, subjects will be randomized in a 1:1 ratio to 1 of the 2 study arms:

- Treatment Arm A: bilateral insertion of LYR-220-32 (7500 µg)
- Treatment Arm B: bilateral sham procedure

Subjects in part 2 of the study will be stratified for treatment assignment according to the following criteria:

• Nasal polyps (Yes vs No)

No more than 10 subjects with polyps will be enrolled in each treatment arm.

On Day 1, after completing any required pretreatment baseline assessments, subjects will receive local anesthetic and may receive decongestants in the ethmoid cavity for endoscopic assessment and in preparation for the insertion procedure.

All subjects will return to clinic for the scheduled follow-up assessments at Day 2 or 3, Day 5 or 8, Week 4, Week 12, Week 16 or 20, and Week 24 visits. Subjects will receive telephone follow-ups at Week 8 and Week 16 or 20 (ie, the week they are not scheduled to attend in-clinic visit for PK blood draw) to record AEs and concomitant medications/procedures that they have had since their last follow-up assessment.

At the Week 24 visit, all subjects will return to clinic for the end-of-treatment (EOT) visit assessments. Subjects who have received LYR-220 will have the bilateral matrices removed using standard surgical tools. Subjects in the sham treatment control arm will have a sham removal procedure.

If **spontaneous dislodgement of LYR-220** occurs before the scheduled Week 24/EOT visit, subjects are required to call the study clinic immediately to report the event. If a subject experiences dislodgement of 1 of the bilateral matrices, the subject will continue in the treatment phase unless an early treatment discontinuation is recommended by the treating physician or subject requests matrix removal from the remaining side of the nose. If matrices spontaneously dislodge from both sides of the nose, the subject will complete an unscheduled **early-termination (ET)** visit within 7 days of the second matrix dislodgement, and complete the assessments scheduled for the Week 24/EOT visit. Spontaneously dislodged LYR-220 should be retained, if available, and returned to the clinic at subject's next visit.

If medically warranted according to the treating physician's discretion (for example, needing sinonasal surgery as rescue treatment), early matrix removal may be performed at an unscheduled ET visit.

Any subject who undergoes an ET visit is required to complete the assessments scheduled for the Week 24/EOT visit and should stay in the study and complete the assessments scheduled for the Week 25 visit within 5-9 days after the ET visit.

4.1.3 Post-treatment Follow-Up Stage

All subjects will undergo a 1-week post-treatment follow-up visit (Week 25 visit). AEs, concomitant medications/procedures, endoscopy, nasal swabs, ophthalmologic assessments, CT, and other scheduled assessments will be performed at Week 25 visit. In addition, subjects will complete a 4-week post-treatment follow-up by telephone or in-clinic visit [Week 28/end-of-study (EOS)]. End of study assessments include AEs, concomitant medications/procedures, and final ePROs (4CS, SNOT-22, CRS-PRO, and End-of-Study Questionnaire).

4.1.4 End of the Trial

The end of the trial is defined as the date of the last EOS visit of the last subject of the study.

4.2 Rationale for Study Design

The primary objective of this study is to evaluate the safety, tolerability, and pharmacokinetics in subjects receiving LYR-220. The study design and endpoints are adequate for assessments of safety and pharmacokinetics of LYR-220 in adult subjects with CRS. The assessments of systemic and local nasal parameters in this study's CRS population and in the context of *in situ* drug delivery via drug matrix are appropriate for safety signal detection. The assessments of plasma MF concentration are sufficient to evaluate drug release profile of LYR-220. The secondary objective of this study is to determine the efficacy of LYR-220 in improving CRS symptoms. A sham treatment arm is added as a control for evaluating the LYR-220 treatment responses against control. The SNOT-22 and CRS-PRO questionnaires have been selected because they are disease specific to analyze quality of life. The 4CS questionnaire is used to evaluate daily cardinal symptoms of CRS subjects. Computed tomography (CT) scan is the gold standard diagnostic radiological tool for CRS and is adequate to evaluate the opacification of ethmoid cavity in the study subject population. The measurement of changes in nasal inflammatory marker levels is appropriate for development and further refinement of study objective endpoints in the clinical program. The safety rationale for the selection of drug dose and polymers in LYR-220 are summarized in the Investigator's Brochure (IB).

4.3 Discontinuation of Study Subjects

Subjects will be encouraged to complete the study through the post-treatment follow-up period. Each subject is free to discontinue from the study at any time, for any reason, and without penalty or loss of benefit. Participation in the study treatment may be discontinued for any of the following reasons:

- Occurrence of any medical condition or circumstance that exposes the subject to substantial risk and/or does not allow the subject to adhere to the requirements of the protocol, including early removal of LYR-220 (Section 6.5).
- Any serious AE (SAE, Section 8.3.11.2), clinically significant AE, severe laboratory abnormality, intercurrent illness, or other medical condition that indicates to the Investigator that continued participation is not in the best interest of the subject.
- Subject's decision to withdraw.
- Requiring sinonasal surgery as rescue treatment.
- If deviations to the use of prohibited medications occur during run-in and study treatment periods, the Investigator, in consultation with the Sponsor and Sponsor's medical monitor will decide on a case-by-case basis whether the subject may continue in the study based on the time the prohibited medication was administered and its pharmacology.
- Subject's failure to comply with protocol requirements or study related procedures.
- Termination of the study by the Sponsor or a regulatory authority that has provided approval to proceed.

Subjects who withdraw or are withdrawn from the study treatment will be requested to return to the clinic for the assessments and procedures scheduled for the EOT and EOS visits (Section 8.1).

The Investigator or study staff will document the reason(s) for subject discontinuation on the electronic Case Report Form (eCRF), notify the EC/IRB as required by their Institution's procedures, and notify the Sponsor of the reason for discontinuation.

4.4 Criteria for Study Termination

If the Sponsor, the Investigator, the medical monitor, EC/IRB, and/or appropriate regulatory officials discover conditions arising during the study that indicate the study should be halted or that the study center should be terminated, appropriate action may be taken after consultation among (at a minimum) the Sponsor, the EC/IRB, and the medical monitor. Refer to Section 10.13 for additional information.

5. SELECTION OF SUBJECTS

5.1 Subject Screening

All subjects evaluated for participation in this study will be screened for study eligibility. A delegated member of the Institution's research team will review the subject's medical history to screen for study eligibility. All subjects who meet initial eligibility requirements will be asked to participate in the study. Each subject will indicate his or her willingness to participate in the study by signing an EC/IRB-approved informed consent form (ICF).

Each subject will be assigned a unique subject identification number upon signing informed consent. Subjects who are assigned a subject ID but do not meet the eligibility criteria will be considered Screen Failures.

If the Investigator believes rescreening is warranted, a subject can be rescreened. Subject identification numbers assigned to subjects who fail screening should not be reused. Investigators must account for all subjects who sign an ICF. If the subject is found to be not eligible at this visit, the investigator/designee should still complete the applicable electronic case report forms (eCRFs).

Subjects who fail screening due to administrative reasons (eg, visit window) or another screening assessment may be allowed to repeat certain screening assessment(s) and re-establish eligibility. Documentation of the decision will be filed in the subject's file.

5.2 Subject Informed Consent

Prior to enrollment in the study, all subjects must review and complete an EC/IRB-approved ICF. All potential subjects must complete the consent process prior to undergoing procedures performed specifically for this study that are outside the standard of care for the institution. Failure to obtain a signed ICF renders the subject ineligible for the study. Sites will comply with ICH Guidelines for obtaining informed consent.

5.3 Inclusion Criteria

A subject must meet all of the following criteria to be eligible for this study:

- 1. Age ≥ 18 years.
- 2. Diagnosed as having CRS, defined by duration of 12 weeks or longer with 2 or more of the following symptoms:
 - nasal blockage/obstruction/congestion
 - nasal discharge (anterior, posterior, or both)
 - facial pain/pressure
 - reduction/loss of sense of smell
- 3. Has had a prior bilateral ethmoidectomy involving both anterior and posterior ethmoids (>3 months ago). NOTE: The postsurgical ethmoid cavity should be large enough to accommodate the LYR-220 matrix.
- 4. Has \geq 5% opacification in the ethmoid cavity on each side on CT.
- 5. SNOT-22 \geq 20 at Screening visit.

- Mean 3CS score over the preceding 7 days of ≥4.5 (on a 0-9 scale for the total 3CS symptoms score) determined within 7 days of Day 1 (the determination for eligibility can be made on any day from Day -7 through Day 1).
- 7. Not currently using INCS or decongestants at Screening or able to cease use of INCS and decongestants from Screening through the duration of the study.
- 8. Ability to tolerate local anesthesia.
- 9. Has been informed of the nature of the study and has provided written informed consent as approved by the Institutional Review Board (IRB)/Ethics Committee (EC) of the respective clinical site or regulatory authority if applicable by national law.
- 10. Agrees to comply with all study requirements.

5.4 Exclusion Criteria

A subject who meets any of the following criteria will be excluded from this study:

- 1. Ethmoidectomy that was unilateral.
- 2. Presence of nasal polyp grade 2 or higher (ie, polyps extending outside of the middle meatus) on either side.
- 3. Endoscopic exclusion criteria at Screening and Day 1 visit:
 - a. Obstructing the nasal cavity for proper placement or retention of LYR-220.
 - b. Dense and obstructing adhesion/synechiae of ethmoid cavity that is difficult to separate or complete adhesion of the middle turbinate to the lateral nasal wall.
 - c. Severe scarring or residual ethmoid cells within ethmoid cavity preventing proper placement of LYR-220.
 - d. Resected or degenerated middle turbinate that could interfere with retention of LYR-220.
 - e. Evidence of mucosal erosion or ulceration within nasal cavity.
 - f. Acute nasal/sinus infection or purulence.
 - g. Evidence of nasal septal perforation.
- 4. Screening CT exclusion criteria:
 - a. Anatomic variation which, in the opinion of the Investigator, would adversely impact placement or retention of LYR-220.
 - b. Structural, noninflammatory related CRS (eg, large concha bullosa, tumor).
 - c. Sinus disease extended into orbital or intracranial space.
 - d. Evidence of mycetoma/fungal ball, allergic fungal rhinosinusitis.
 - e. Sinus mucocele.
- 5. Seasonal allergic rhinitis (SAR) subjects with symptoms and/or, based on time of year, would anticipate onset of symptoms within 24 weeks of Day 1 procedure.
- 6. Perennial rhinitis subjects whose symptoms are well controlled by regular use of INCS.
- 7. With severe asthma or with 1 or more exacerbations of asthma requiring SCS use within the 3 months prior to the Screening visit. Subjects with moderate or severe asthma will also be excluded if they have not been on a stable regimen of inhaled corticosteroids for asthma for a minimum of 3 months prior to the Screening visit.

- 8. History or clinical evidence or suspicion of invasive fungal sinusitis, allergic fungal rhinosinusitis, or atrophic rhinitis.
- 9. Known history of hypersensitivity or intolerance to corticosteroids.
- 10. Oral steroid or monoclonal antibody (Xolair, Nucala, Dupixent) dependent condition, including biologics use within 3 months of screening per protocol clarification letter.
- 11. SCS within 1 month prior to Screening visit.
- 12. Known history of hypothalamic pituitary adrenal axial dysfunction.
- 13. Previous pituitary or adrenal surgery.
- 14. More than 1 episode of epistaxis with frank bleeding requiring medical attention within 2 months of Screening visit or more than 1 episode of epistaxis with frank bleeding within 1 month of Screening visit.
- 15. Acute exacerbation of nasal allergy, CRS, upper respiratory tract infection (URTI), common cold, or clear worsening or acute change in symptoms within 4 weeks of the Screening visit. The infection/exacerbation must be resolved, and antibiotic or other medication use must be discontinued prior to screening per protocol clarification letter.
- 16. Dental procedure/implant on maxillary dentition within 4 weeks of the Screening visit.
- 17. Past or present acute or chronic intracranial or orbital complications of CRS (eg, brain abscess, related problems with eyes or central nervous system).
- History or diagnosis (in either eye) of glaucoma or ocular hypertension (IOP >21 mm Hg).
- 19. Presence (in either eye) of posterior subcapsular cataract of grade 2 or higher, nuclear cataract of grade 3 or higher, or cortical cataract of grade 2 or higher or involving a minimum of center optic zone of 3-mm diameter.
- 20. Loss of functional vision in 1 or both eyes.
- 21. Diagnosed with ongoing rhinitis medicamentosa.
- 22. Known history of immune dysfunction including immune deficiency (IgG subclass deficiency or IgA deficiency) or autoimmune disease (eg, Wegener's granulomatosis, sarcoidosis) that requires immunomodulatory therapy. NOTE: Autoimmune conditions that do not require immunomodulatory therapy are not exclusionary.
- 23. Past, present, or planned organ transplant or chemotherapy with immunosuppression.
- 24. History or diagnosis of ciliary dysfunction (eg, cystic fibrosis, primary ciliary dyskinesia [Kartagener syndrome]).
- 25. Past or present systemic vasculitis (eg, granulomatosis with polyangiitis).
- 26. Evidence of disease or condition expected to compromise survival or ability to complete follow-up assessments.
- 27. Pregnant or breast feeding. Females of child-bearing potential must test negative for pregnancy at the time of Screening based on a serum pregnancy test and reverified on Day 1 prior to the time of treatment based on a urine pregnancy test. Both male and female subjects of reproductive potential must agree to use highly effective methods of birth control, throughout the study.

- 28. Previously received an experimental treatment in another clinical study within 5 halflives or 30 days (whichever is longer) of Screening visit.
- 29. Currently participating in another drug or device study.
- 30. Currently positive for COVID-19 or residual sinonasal symptoms from a previous COVID-19 infection.
- 31. Determined by the Investigator as not suitable to be enrolled for reasons not already specified if the health of the subject or the validity of the study outcomes may be compromised.

6. TREATMENT OF SUBJECTS

6.1 Subject Allocation

6.1.1 Enrollment

Approximately 50 subjects who complete the study Screening assessments and the run-in period and meet all eligibility criteria will be enrolled and treated bilaterally with either the LYR-220-32 design or a sham treatment on Day 1 (as described in Section 4.1).

For any reason, if the Investigator is unable to successfully administer LYR-220 into both ethmoid cavities in a subject (as described in Section 6.2.4), this subject will be considered as an Enrollment Failure.

6.1.2 Randomization (Part 2 Study Only)

Approximately 40 subjects who complete the study Screening assessments and the run-in period, and meet all eligibility criteria on Day 1 in the part 2 of the study will, before any treatment, be randomized in a 1:1 ratio to 1 of the 2 study arms:

- Treatment Arm A: bilateral insertion of LYR-220-32 (7500 µg)
- Treatment Arm B: bilateral sham treatment control

Subjects will be stratified for treatment assignment according to the following criteria:

• Nasal polyps (Yes vs No)

No more than 10 subjects with nasal polyps will be assigned to each treatment arm. Treatment will be assigned according to a randomization scheme generated by the Sponsor or designee. Randomization will be conducted using Interactive Response Technology (IRT).

6.2 Study Product Administration

6.2.1 **Pre-procedure Medication**

Prior to LYR-220 administration, all subjects will receive local anesthetic and decongestants in the ethmoid cavity for endoscopic assessment and in preparation for the insertion procedure according to the individual clinic/site standards.

6.2.2 Study Product Preparation

LYR-220 and sham products will be provided to the study site as described in Section 7.2.1. Preparation of LYR-220 and the sham product should be performed in accordance with the instructions for use (IFU) provided in a separate document and should not start until the subject has been prepared, anesthetized, and is ready for the insertion procedure.

6.2.3 Study Product Administration

LYR-220 is designed to be administered intranasally under endoscopic visualization. Subjects who are assigned to either design of LYR-220 will have LYR-220 administered bilaterally into the ethmoid cavity. Subjects who are assigned to the sham procedure arm, will undergo bilateral mock administration (ie, sham procedure), consisting of a bilateral insertion of an applicator (without LYR-220 matrix) into the ethmoid cavity until the applicator tip touches the posterior

wall of the ethmoid cavity for a minimum of 20 seconds, followed by withdrawal of the applicator. To maintain subject blinding to the treatment assignment in part 2 of the study, subjects will wear an eye mask (ie, blindfold) and ear/headphones at the time of the LYR-220 administration/sham procedure. A Sponsor representative/case manager may be present during Day 1 visit to provide guidance regarding product administration.

Following administration procedure, all enrolled subjects should be monitored to ensure there is no epistaxis or any other untoward conditions that requires medical attention. Subjects should remain in/around the clinic and complete any further assessments (such as the 1-hour post procedure PK blood draw) until they are cleared to leave by the study clinic personnel.

6.2.4 Enrollment Failure

The Investigator will be allowed up to 2 attempts at LYR-220 administration per side. If the Investigator is unable to administer LYR-220 bilaterally into both ethmoid cavities of a subject, the Investigator will remove any LYR-220 already administered and treat the subject with any appropriate therapy, if necessary. The subject will be considered as an **Enrollment Failure**. Follow-up with subjects will occur within 7 (\pm 2) days by telephone for AE and concomitant medication assessments.

6.2.5 End of Day 1 Visit

Prior to discharge at Day 1 visit, the study staff will remind enrolled subjects of the following:

- That they are currently enrolled in an investigational study for up to 6 months.
- To avoid nose blowing for the rest of the day post procedure.
- To wipe or gently blow their nose during the treatment stage.
- To sneeze with an open mouth to avoid over-pressurization to the nose.
- To call the study clinic if they have any unexpected epistaxis.
- To call the study clinic immediately should the subject experience severe discomfort or if LYR-220 falls out of the nose.

6.3 Blinding

Subjects should remain blinded to their treatment assignment until the final study database is locked. To maintain subject blinding (LYR-220 or sham) in part 2 of the study, each subject will wear an eye mask (ie, blindfold) and ear/headphones at the time of the LYR-220 administration/sham procedure and at all post Day 1 visits (scheduled or unscheduled) during any endoscopy assessments and during the LYR-220 administration/sham removal procedure.

6.3.1 Procedures for Breaking the Blind Prior to Study Completion

Breaking the blind is expressly forbidden except in the event of spontaneous dislodgment of LYR-220, or a medical emergency where the identity of the treatment assignment must be known in order to properly treat the subject. If breaking the blind is required because of a medical emergency, decision to unblind lies solely with the investigator.

In all cases where the code is broken, the Investigator must record the date and reason for code breaking.

6.4 Prior and Concomitant Medications

Subjects participating in the study are free to use any appropriate concomitant medications if medically warranted per treating physician's discretion. However, a standardized concomitant medications regimen is recommended during the run-in and treatment stages to avoid confounding the safety, pharmacokinetic, and efficacy assessments of LYR-220.

6.4.1 **Prior Medications**

Beginning at Screening, all medications and other treatments taken by subjects will be recorded on the concomitant medications CRF. In addition, all subjects will be required to refrain from use of prohibited medications (Section 6.4.2) beginning at Screening.

Subjects may be permitted to continue medications that do not meet exclusionary criteria (Section 6.4.3). If any additional concomitant medications are to be administered during the study, or a dose adjustment is required for any existing concomitant medication, the Investigator may contact the Sponsor's medical monitor for guidance prior to administration as needed, provided the safety of the subject would not be compromised.

6.4.2 Prohibited Concomitant Medications

Use of the following medications is prohibited for the duration of the study:

- Any drug or product containing mometasone furoate (MF).
- Oral/ocular/intramuscular/intravenous/intranasal corticosteroids (except for oral corticosteroids permitted as rescue medication only).
- Anti-allergy medications, including: first generation antihistamines (eg, diphenhydramine, dimenhydrinate, chlorpheniramine), leukotriene receptor antagonists (except for a stable regimen for asthma), nasal cromolyn sodium or sodium cromoglycate, nedocromil sodium, atropine, ipratropium bromide, or guaifenesin.
- Oral/intranasal decongestants (except for short course of intranasal decongestants permitted for severe acute nasal blockage or during endoscopic procedures).
- Inhaled anticholinergic medications (except for a stable regimen for subjects with chronic obstructive pulmonary disease [COPD]).
- Any potent cytochrome P-450 3A4 (CYP3A4) inhibitors (eg, ketoconazole and ritonavir).
- Any monoclonal antibody.
- Any allergen immunotherapy (except for a stable dose and regimen).
- Oral anti-fungal medication.

Subjects who received prohibited medications will be considered to have a protocol deviation and may require withdrawal from the study.

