10.6 Protocol Deviations

The investigator agrees to conduct the study according to the clinical protocol and agrees that all persons delegated to perform study procedures will do so as well. An investigator is not permitted to deviate from the protocol without the prior written approval of the Sponsor unless there are concerns of subject's safety. Under emergency circumstances, deviations from the protocol to protect the rights, safety, and well-being of human subjects may proceed without prior approval of the Sponsor and the EC/IRB. Such deviations shall be documented and reported to the Sponsor and the EC/IRB (as required) as soon as possible.

A protocol deviation is a failure to comply with the requirements specified within this clinical study protocol. Examples of protocol deviations may include enrollment of a study subject who does not meet all of the inclusion/exclusion criteria specified in the protocol, visits performed outside of the protocol specified visit window, and missed study visits. Each site investigator shall conduct this clinical study in accordance with this clinical study protocol, local regulatory authority regulations, GCP, and any conditions of approval imposed by their EC/IRB.

The investigator agrees to inform the EC/IRB of all protocol deviations according to institutional requirements. The occurrence of protocol deviations will be monitored by the Sponsor personnel or designee on an ongoing basis. Deviations from the protocol include, but are not limited to, the use of prohibited medications or therapies and out of window visits. All protocol deviations should be documented and explained. Major protocol violations are defined as those that could impact the performance evaluation such as a subject is ineligible, missing key data, received an

unauthorized treatment. All subjects with protocol deviations will continue to be followed for safety and performance assessments.

If an investigator is found to be repeatedly noncompliant with the Clinical Trial Research Agreement, study protocol or any other conditions of the clinical study, the Sponsor at its sole discretion, will either undertake remedial measures to secure compliance or terminate the investigator's participation in the study.

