## Intercurrent events (ICE) and strategy

- (1) ICE1: Rescue treatment: efficacy data collected after rescue treatment will not be used (Hypothetical Strategy)
- (2) ICE2: Premature treatment discontinuation: efficacy data collected after treatment discontinuation will be included in the analysis regardless of attribution to treatment (Treatment Policy Strategy)

If both ICE1 and ICE2 occur for the same subject, addressing ICE1 takes precedence over ICE2. For example, if a subject took rescue medication at Week 10, and subsequently dropped out at Week 12 with no score at Week 24, then the method addressing ICE1 will be used.

3.4.2.1.2 Statistical Analysis for CFBL in SNOT-22 Total and Subdomain Scores 3.4.2.1.2.1 Part 1

Descriptive summary statistics on the values and changes from baseline will be presented for the SNOT-22 total and subdomain score at each analysis visit by treatment group.

3.4.2.1.2.2 Part 2

Statistical analysis of the CFBL in SNOT-22 total and subdomain scores at Weeks 2, 4, 6, 8, 12, 16, 20, 24, and 28/Follow-up will be carried out based on the Efficacy Analysis Set.

MMRM model without imputation: analysis will be carried out using MMRM model with the CFBL in SNOT-22 score as the dependent variable, and include the fixed, categorical effects of treatment, visit, treatment-by-visit interaction, and nasal polyp stratum as well as the continuous, fixed covariates of baseline score and baseline scoreby-visit interaction. An unstructured covariance structure shared across treatment groups will be used to model the within-subject errors. The covariance parameters in the above model will be fitted through a working model that assumes joint multivariate normality (MVN) of responses by maximizing the restricted likelihood (REML) under the working model, and the mean parameters will be estimated by generalized least squares after plugging in REML estimate of covariance parameters. In case the model does not converge with the unstructured covariance structure, the heterogenous Toeplitz structure (TOEPH) will be used instead. In case the model will not converge with the TOEPH structure, heterogenous compound symmetry (CSH) will be used instead. The Kenward-Roger approximation will be used to estimate denominator degrees of freedom and adjust nominal standard errors based on the inverse observed information from the working MVN model. Missing data will be handled by the MMRM under the missing at random (MAR) assumption.

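### Protocol 6.4.2 and 4.3 allow withdrawal from the study after prohibited medication, which conflicts with 10.6 and lets loss of follow-up depend on outcome and arm

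*Protocol*

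**What the plan says.** Protocol 6.4.2, and the synopsis in the same words, classes prohibited-medication use as a deviation that can end a subject's participation: "Subjects who received prohibited medications will be considered to have a protocol deviation and may require withdrawal from the study".

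Protocol 4.3 says who decides and on what grounds. The decision lies with "the Investigator, in consultation with the Sponsor and Sponsor's medical monitor", who "will decide on a case-by-case basis whether the subject may continue in the study based on the time the prohibited medication was administered" and on the drug's pharmacology. SAP 2.2.4 carries the same bullet. The list containing it is introduced as reasons for stopping study treatment, but this bullet is about staying in the study.

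Protocol 10.6 gives use of prohibited medications or therapies as an example of a deviation and then states, without exception: "All subjects with protocol deviations will continue to be followed for safety and performance assessments".

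For efficacy, the SAP names two intercurrent events: rescue treatment and premature treatment discontinuation. For the second it adopts a treatment-policy strategy, under which "efficacy data collected after treatment discontinuation will be included in the analysis regardless of attribution to treatment".

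**The concern.** A site with a subject who has taken a prohibited drug finds one section that permits ending participation and another that requires follow-up to go on. Sites may resolve this differently, and the choice determines whether later scores and adverse events exist at all.

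The choice need not be neutral. The prohibited list includes intranasal corticosteroids, decongestants beyond the permitted short course, and monoclonal antibodies. Inclusion criterion 7 requires subjects to be off intranasal steroids and decongestants from Screening onward, so a return to them by a poorly controlled subject is foreseeable. The site investigator is not described as blinded. If such subjects leave the study, the missing scores may come disproportionately from poor courses in one arm. The treatment-policy strategy cannot use data that were never collected.

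**Working it through.** **1. Do the passages cover the same subjects?** Yes. Section 6.4.2 makes prohibited-medication use a deviation, 10.6 names the same use as a deviation, and 10.6 applies to all subjects with deviations. Withdrawal from the study under 6.4.2 is therefore incompatible with 10.6. Other text points towards keeping subjects. Section 6.5 gives use of another mometasone product as an example of a reason for early matrix removal. Section 4.1.2 then has subjects with an early-termination visit remain in the study and complete the Week 25 assessments.

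**2. Can the decision be related to arm?** Only subjects are covered by the blinding section: "Subjects should remain blinded to their treatment assignment until the final study database is locked". The investigator performs the insertion ("The Investigator will be allowed up to 2 attempts at LYR-220 administration per side", Protocol 6.2.4), and the sham applicator holds no matrix (6.2.3). The only blinded assessor named is the eye examiner (8.3.5). That the investigator knows the arm is an inference from the procedure, though a firm one.

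**3. What happens to the lost scores?** Rescue in SAP 3.1.4.11 means systemic corticosteroids or sinonasal surgery. Intranasal steroids, decongestants and monoclonal antibodies are not rescue, so the worst-score imputation for post-rescue data does not reach them.

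| Endpoint in Part 2 | Handling of non-rescue missing scores |
|---|---|
| SNOT-22, 3CS, individual symptoms | MAR in both MMRM analyses and in the multiple-imputation ANCOVA; LOCF in one further ANCOVA, Weeks 24 and 28 only |
| CRS-PRO total, PGIS | MAR in the MMRM; no other model |

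**4. How large could it be?** The documents give no effect size, SD or drop-out rate, and the sample size is not based on power. There is no plan figure to reproduce. What follows is an illustration under assumptions.

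- Input from Protocol 4.1: 20 subjects per arm. Assumed: standard normal outcomes, with the worst k of 20 in one arm lost.
- Standard error of the difference: √(1/20 + 1/20) = 0.316 SD.
- Effect detectable with 80% power at one-sided 0.05: (1.645 + 0.842) × 0.316 = 0.79 SD.
- MAR-adjusted mean: observed mean + slope × (earlier-visit mean of all 20 − earlier-visit mean of those observed), using one earlier visit with assumed correlation 0.5 or 0.7.

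Shift in that arm's mean, in SD, averaged over 40,000 simulated trials:

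| Lost, of 20 | No adjustment | MAR, correlation 0.5 | MAR, correlation 0.7 |
|---|---|---|---|
| 1 | 0.10 | 0.08 | 0.06 |
| 2 | 0.18 | 0.14 | 0.11 |
| 3 | 0.26 | 0.21 | 0.16 |
| 4 | 0.33 | 0.28 | 0.21 |

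The affected arm looks better than it is. If that arm is sham, the treatment difference shrinks; if it is LYR-220, the difference grows. Selecting exactly the worst subjects is the extreme case, not a forecast.

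**The case against.** A reader might infer that unblinded investigators alone decide who drops out, and do so on outcome. The documents do not support that. Section 4.3 requires consultation with the Sponsor and its medical monitor, the stated grounds are timing and pharmacology, and SAP 2.2.2 records a Sponsor blind in Part 2. The list also contains drugs with no obvious link to CRS control, such as CYP3A4 inhibitors and oral antifungals. A link to outcome and arm is possible and plausible, but it is not stated.

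Uncontrolled CRS also has its own route: rescue with oral corticosteroids or surgery, which is an intercurrent event with a defined strategy. Short-course oxymetazoline and non-sedating antihistamines are permitted. Many poor courses may therefore never pass through 6.4.2.

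Section 4.3 can be read as concerning treatment only. Its list opens that way, and it closes by asking subjects taken off treatment to return for the EOT and EOS assessments. This softens the conflict in 4.3 but not in 6.4.2, which refers to the study. The return request also covers two visits, not daily symptom scores or intermediate questionnaires.

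Finally, MAR is not the only handling. The LOCF ANCOVA is a real check for SNOT-22 and cardinal symptoms. It is a partial one: it covers Weeks 24 and 28, it carries forward whatever was last seen before withdrawal, and it is not planned for CRS-PRO or PGIS.

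**Conclusion.** The conflict between 6.4.2, the synopsis, 4.3 and SAP 2.2.4 on one side and 10.6 on the other is real and should be resolved. Following the withdrawal wording would discard data that the SAP's strategy for treatment discontinuation is meant to use, and the loss can be related to outcome and arm.

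The size is unknown. The illustration shows that the loss of a few subjects could matter at 20 per arm: 0.06 to 0.28 SD after adjustment, against a standard error of 0.316 SD. It rests on assumed correlations and worst-case selection, and it does not show that bias occurred or in which direction.

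The effect is confined to secondary efficacy endpoints and to completeness of safety follow-up, in a trial whose primary endpoint is safety. It would go too far to say that safety follow-up to Week 28 is lost. An EOS return is requested after treatment withdrawal, and adverse events that lead to early termination or are related to product or procedure are followed to resolution or stabilization (Protocol 8.3.11.1). What is at risk is full collection of other events in subjects who leave the study.

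**What to change.** Reconcile Protocol 6.4.2, 4.3, the synopsis and SAP 2.2.4 with Protocol 10.6 by separating study treatment from study participation.

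- For subjects already treated on Day 1, state that scheduled ePRO and safety data collection continues, as 10.6 already provides, unless consent is withdrawn. Record the prohibited drug and its dates.
- Handle deviations during run-in separately, as an eligibility matter. The 4.3 bullet covers run-in as well as treatment, and a run-in subject has no study treatment to stop, so one treatment-only wording would not fit both.
- Leave any decision on study treatment with the clinical team. No clinical rule is proposed here.

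The cost is wording in those places and a memo to sites. No new visits or assessments are needed.
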